4.1.1. Part 1 (SAD)

Part 1 is a single ascending dose (SAD) study to assess the safety, tolerability and PK of single doses of ZP-059 in 4 cohorts of healthy male and female subjects. Each cohort will comprise 6 subjects (planned total of 24 subjects). An evaluable subject for Part 1 (SAD) of the study is defined as a subject who has received a dose of ZP-059 and has sufficient data for evaluation of the safety and PK objectives as outlined in $\frac{\text{Section 3.1.1}}{\text{Section 3.1.2}}$ and $\frac{\text{Section 3.1.2}}{\text{Section 3.1.2}}$, respectively.

An additional cohort of 6 subjects (Cohort 5) may be enrolled if it is deemed appropriate to repeat a dose level, assess an interim dose level or assess a dose level higher than planned (Section 6.6.1). Single doses will not exceed 40 mg of ZP-059 based on safety margins calculated following non-clinical studies (Section 4.3). For each dose escalation, the dose increase will not be more than 3-fold. A repeat dose level or higher dose level will only be assessed provided no dose escalation or study stopping criteria have been met.

Eligible subjects will receive a single dose of ZP-059 on the morning of Day 1. Subjects will be required to fast (water permitted) for at least 1 hour prior to each dose and 1 hour post each dose.

ZP-059 is a first in human IMP and therefore an additional safety precaution has been considered for dosing in each cohort and dose level for Parts 1 and 2. For the first 2 subjects in each cohort, there will be a minimum interval of 20 minutes between dosing. After the second subject is dosed there will be at least a 30 minutes observation period before the remaining 4 subjects are dosed. The remaining subjects will be dosed if the first two subjects show no clinically significant safety or tolerability concerns (including vital signs measurements, spirometry, physical examinations (symptom directed if required) and review of any adverse events [AEs] including any acute side effects e.g. excessive coughing) at the discretion of the investigator. Any clinically significant findings from the first two subjects in the opinion of the investigator will be discussed with the Sponsor prior to dosing of the remaining 4 subjects. The dosing interval between dosing subjects in the remainder of the cohort will be at the discretion of the investigator (in consultation with the sponsor if required) i.e. this could be increased or decreased as appropriate.

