9.4.1. General considerations

For study parts 1 and 2, background and demographic characteristics and safety data will be summarised by ZP-059 dose and overall doses. PK data will be summarised by ZP-059 dose only.

For study part 3, background and demographic characteristics will be summarised by treatment sequence and overall. Safety and PK data will be summarised by treatment: Test (ZP-059) or Reference (oral voriconazole).

Full details of the statistical analyses will be provided in a separate statistical analysis plan (SAP), which will be finalised before database lock.

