# **Modification History**

Version	Change History	Reason	Date 12AUG2020
1.0	First Version	N/A	
2.0	
 
Update to protocol deviations listing to only important PDs
 
Removed exposure table from analysis
 
Updated AESI to tabulate if necessary
 
Added Sputum plug and processed sputum to analysis
 
	
 
To bring in line with SQN current processes
 
Following client review of dry run TFL
 
	280CT2020

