## 2 CHANGES FROM THE PROTOCOL PLANNED ANALYSIS

For the PK analysis, linearity ratios will not be reported due to the likelihood that  $AUC_{0-}$  inf cannot be obtained.

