## 3.2 Study Endpoints

#### 3.2.1 **Primary Endpoints**

The primary endpoint for each Part (Part 1, 2, & 3) of the study is:

 Safety and tolerability, as assessed by monitoring of adverse events (AEs), physical examinations, changes in vital signs, clinical laboratory parameters, electrocardiogram (ECG), pulse oximetry and spirometry assessments (forced expiratory volume in 1 second (FEV1), forced vital capacity (FVC), peak expiratory flow rate (PEFR) and FEV1/FVC).

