## 7.5 Data presentations

#### 7.5.1 Parts 1 & 2 Specific Presentations

For each study part, safety and PK data will be summarised by ZP-059 dose only and all other data will be summarised in tabular form by ZP-059 dose group and overall.

Listings will be sorted by study part, ZP-059 dose group, screening number and date/time of assessment.

Dose groups will be presented in the following order using these labels:

- ZP-059 5mg
- ZP-059 XXmg, etc.

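### SAP 7.5.1 drops the protocol's all-doses safety summary for Parts 1 and 2 without declaring the change, so the primary endpoint is tabulated only in dose columns of about 6 planned subjects

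*SAP*

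**What the plan says.** Protocol 9.4.1 treats safety and PK differently in Parts 1 and 2. For safety: "safety data will be summarised by ZP-059 dose and overall doses". The next sentence narrows PK alone: "PK data will be summarised by ZP-059 dose only".

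SAP 7.5.1 puts the two together: "safety and PK data will be summarised by ZP-059 dose only". The same sentence keeps the pooled presentation for everything else: "all other data will be summarised in tabular form by ZP-059 dose group and overall".

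SAP section 2 declares a single change, which concerns PK: "For the PK analysis, linearity ratios will not be reported due to the likelihood that" AUC to infinity cannot be obtained. The modification history for SAP version 2.0 covers the deviations listing, tabulation of adverse events of special interest, sputum and exposure ("Removed exposure table from analysis"). It does not mention the safety columns.

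On the standing of safety, SAP 3.2.1 begins "The primary endpoint for each Part (Part 1, 2, & 3) of the study is" and names safety and tolerability. On cohort size, Protocol 4.1.1 says for Part 1: "Each cohort will comprise 6 subjects (planned total of 24 subjects". Protocol 4.1.2 plans 18 subjects in Part 2, again in cohorts of 6.

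**The concern.** The SAP is the document from which the tables are programmed. It removes a summary of the primary endpoint that the protocol had fixed, while demographic and other background data keep theirs. A reader who consults SAP section 2 to learn how the analysis departs from the protocol will not find this departure.

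The practical loss is the pooled display of adverse events, laboratory values, vital signs, ECG, spirometry and oximetry over all ZP-059 doses within a part. A column of 6 says little about an uncommon event. For continuous measures, SAP 7.1 specifies medians and quartiles, and a pooled median or quartile of change from baseline cannot be obtained by combining the dose columns.

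**Working it through.** **1. Reproduce the planned numbers.** Inputs are from Protocol 4.1.1, 4.1.2 and 9.2 and SAP section 4.
- Part 1: 4 × 6 = 24; with one optional cohort, 24 + 6 = 30.
- Part 2: 3 × 6 = 18; with two optional cohorts, 18 + 12 = 30.

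These match the stated totals. There is no power calculation to reproduce, since both documents say the study is not powered for any formal test.

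**2. Compare the presentation rules for Parts 1 and 2.**

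| Data | Protocol 9.4.1 | SAP 7.5.1 |
|---|---|---|
| Safety | by dose and over all doses | by dose only |
| PK | by dose only | by dose only |
| Background and demographic | by dose and over all doses | by dose group and overall |

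Only the safety row differs. The SAP's restriction to dose alone leaves no reading of 7.5.1 under which the pooled safety summary survives.

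**3. Look for a declaration.** SAP section 2 has one item (linearity ratios). The version 2.0 history has four, none on this. SAP section 1 says the plan is based on the protocol through amendment 2, so a protocol change does not explain the difference.

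**4. Look for a total elsewhere in the SAP.** SAP 7.13.1.1 orders system organ classes and preferred terms by descending total number of subjects with TEAEs. That implies a total is computed for sorting, but no section specifies an overall safety column. The table shells are a separate document and were not available to check.

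**5. Illustrate the denominators.** With no events in n subjects, the exact one-sided 95% upper bound on the event rate is 1 − 0.05^(1/n). The chance of seeing at least one event at true rate p is 1 − (1 − p)^n. The documents give no expected rate, so 5%, 10% and 20% are assumptions.

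| n | Where it arises | Zero-event bound | p = 5% | p = 10% | p = 20% |
|---|---|---|---|---|---|
| 6 | one planned cohort | 39.3% | 26.5% | 46.9% | 73.8% |
| 18 | Part 2, all doses | 15.3% | 60.3% | 85.0% | 98.2% |
| 24 | Part 1, all doses | 11.7% | 70.8% | 92.0% | 99.5% |
| 30 | either part with all optional cohorts | 9.5% | 78.5% | 95.8% | 99.9% |

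For comparison, the ZP-059 column in Part 3 has 16 planned subjects: 1 − 0.05^(1/16) = 17.1%, and 1 − 0.9^16 = 81.5% at p = 10%.

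The figure of 6 is the planned cohort size. With 4 subjects, the minimum number evaluable, the bound is 52.7%. With 12, if an optional cohort repeats a dose, it is 22.1%.

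**The case against.** The strongest reply is that little information is lost. Each subject in Parts 1 and 2 belongs to one dose group, and Part 2 excludes anyone who has already received study drug in this trial (exclusion criterion 5). The dose columns are therefore disjoint, and the pooled count for any adverse event is the sum along the row. SAP 7.13.1.3 also lists every event with treatment-emergent and special-interest flags. This stands for event counts. It does not hold for pooled medians and quartiles of spirometry, ECG or laboratory changes, which would have to be recalculated from the listings.

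A reader might infer that the pooled column is the only place where enough subjects are exposed to say anything about airway, visual or hepatic events, or that safety rates can now be estimated only at n=6. The documents do not support that. SAP 7.5.2 summarises Part 3 safety by treatment, giving 16 planned subjects on one ZP-059 dose, and an optional cohort may enlarge a dose group in Part 1 or 2.

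Nor does the plan estimate event rates. The protocol synopsis rules out formal analysis of safety data, so the overall column would not itself have carried the bounds above. Those bounds also assume one rate across doses rising from 5 mg towards a 40 mg cap and, in Part 2, possibly across once- and twice-daily regimens. If toxicity rises with dose, a pooled rate describes no dose and can dilute a signal at the top. That is a reason to keep the dose columns beside the pooled one, as the protocol does.

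It is also fair to say that dose escalation is unaffected: the safety advisory committee reviews cohort data, and SAP section 6 says the statistics group produces no outputs for those reviews. Finally, Protocol 9.4.1 leaves full details to the SAP. That permits elaboration, but not an unannounced reversal of a rule the same section states.

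**Conclusion.** The point holds as an undeclared departure of the SAP from the protocol in how the primary endpoint is presented in Parts 1 and 2. Its size is one pooled descriptive summary per part, with 24 planned subjects in Part 1 and 18 in Part 2, replaced by columns of about 6. The zero-event bounds of 39%, 15% and 12% show what those denominators mean under a common event rate; they do not measure information lost. The sort rule in SAP 7.13.1.1 makes a drafting slip plausible, but the text does not settle whether the omission was intended. The conclusion rests on the SAP text; the shells might already contain an overall column, in which case only the wording needs correcting.

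A reader might also want the pooled summary split by once- and twice-daily dosing in Part 2. Protocol 9.4.1 does not mention regimen, so that would be a separate proposal and not part of restoring the protocol rule.

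**What to change.** In SAP 7.5.1, replace the combined rule with: *safety data will be summarised by ZP-059 dose and overall; PK data by ZP-059 dose only*. Add the overall column beside the dose columns in the Part 1 and Part 2 safety tables and shells. If the omission is deliberate, state it in SAP section 2 with the reason.

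No new data or added exposure is needed. The modification history shows that dry-run tables had already been reviewed by version 2.0, so the cost is a small amount of reprogramming and QC of existing outputs as well as the edit to the text.

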#### 7.5.2 Part 3 Specific Presentations

Safety and PK data will be summarised by treatment group and all other data will be summarised in tabular form by treatment sequence and overall.

Listings will be sorted by treatment or treatment sequence as appropriate, screening number and date/time of assessment.

Treatment groups will be presented in the following order using these labels:

- ZP-059
- Oral Voriconazole

Treatment sequences will be presented in the following order using these labels:

- ZP-059 / Oral Voriconazole
- Oral Voriconazole / ZP-059

#### 7.5.3 General Presentations

Graphical presentations of the data will also be provided where appropriate.

Only scheduled post-baseline assessments will be tabulated; post-baseline repeat/unscheduled assessments will not be tabulated, although they will be listed.

Eligibility, screen failures and analysis sets will be summarised using the Screened set. Background and demographic characteristics, study completion/withdrawal, and protocol deviations will be summarised using the Enrolled Set. Prior/concomitant medications, administration of study treatment and exposure and safety will be summarised using the SAF.

All other data will be summarised using the SAF apart from PK, which will be summarised using the relevant PK sets.

Eligibility and screen failures will be listed using the Screened set. Completion/withdrawal and analysis set listings will be based on the Enrolled set. PK listings will be based on the PK sets. Safety listings will be based on the SAF set. All other listings will be based on the Enrolled set.

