- c. Height and Weight at screening. Weight only on Day 1 (pre-dose) of each treatment period.
- d. All female subjects.
- e. Of the relevant treatment period only, training will be performed pre-dose on Day 1.
- f. Full physical examination at screening Study Day 5 and Study Day 9. Symptom directed examination; if required at any other visits or times at the discretion of the investigator.
- g. Clinical safety laboratory samples (clinical chemistry, haematology and urinalysis) must be performed within 7 days of Day 1, Period 1; if this interval is exceeded, sampling must be repeated. There is no requirement for Day 1 pre-dose laboratory assessment results to be available before dosing in either Period 1 or Period 2. Samples for clinical chemistry will be obtained following a fast of at least 8 hours (water permitted).
- h. Performed in triplicate. For assessment of time windows, the time of the first ECG of the triplicate will be used.
- i. Systolic and diastolic blood pressure, pulse rate and respiratory rate.
- j. Pre and post bronchodilator (salbutamol) reversibility testing at screening. At all other visits and time-points spirometry may be performed pre or post bronchodilator; i.e. there are no requirements for bronchodilator restrictions after the screening visit.
- k. Screening sputum samples will be collected for assessment of eligibility only and will not be analysed.
- A minimum of 6 out of the 16 subjects to be randomised in Part 3 must provide a sufficient sputum sample at screening as per inclusion criteria 13.
- m. Subjects will undergo a SARS-COV-2 RT-PCR test prior to sputum induction at screening. Subjects testing negative may proceed to enrol in the study, provided other eligibility criteria are met; Subjects who test positive should be withdrawn from screening for the study and undergo or be referred for appropriate medical care as determined by local policy for managing a positive result. SARS-COV-2 RT-PCR test must be performed within 14 days of Day 1, Period 1. If this interval is exceeded, sampling must be repeated. Additional RT-PCR testing may be performed throughout the study if deemed necessary by the investigator.
- n. Inhaler device training at screening is to be a demonstration only.

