7.1. Discontinuation of Investigational Medicinal Product

Subjects will be withdrawn from IMP for the following reasons:

- Subjects will be withdrawn from IMP if they exhibit a SAE and/or any AEs that in the opinion of the PI may jeopardise their safety.
- QTcF interval of >500 msec or increase in QTcF interval of >60 msec from baseline.
 - For the purpose of QTcF withdrawal criteria, baseline will be considered as the mean pre-dose Day 1 measurement for Parts 1 and 2, and the mean pre-dose Day 1 measurement of each treatment period for Part 3 (i.e. baseline for Period 1 is pre-dose on Day 1 Period 1; baseline for Period 2 is pre-dose on Day 1 Period 2). The withdrawal criterion will be assessed against the mean QTcF of triplicate ECGs and confirmed by a repeat triplicate ECG. ECGs will be performed within a time window of 5 minutes, with minimum of 1 minute between subsequent ECGs
- Increase of total bilirubin greater than or equal to 3x the upper level of normal
- Increase of liver enzyme (AST, ALT) value greater than or equal to 3x the upper level of normal. Asymptomatic subjects with a liver enzyme [AST, ALT] greater than or equal to 2x the upper level of normal but less than or equal to 3x the upper level of normal will be retested, as required.
- Pregnancy of a female subject or female partner of a male subject
- Upon the subject's request (withdrawal of consent)
- Significant deviation from the protocol that is considered, in the opinion of the investigator or sponsor, to jeopardise the subject's safety
- Requirement for prohibited medication
- At the discretion of the investigator
- Termination of the study for any reason by the sponsor.
- Parts 1 only: Any drug-induced bronchoconstriction requiring treatment
- Part 2 and 3 only: Exacerbation of asthma requiring systemic treatment

For a subject who withdraws or is withdrawn every effort will be made to ensure the subject completes early discontinuation procedures (if applicable) as soon as possible after discontinuation and as detailed in the study schedule of activities (SOA) in Section 1.2.2 (Part 2) and Section 1.2.3 (Part 3). A safety follow-up call will also be performed, if possible, if the early discontinuation visit has been performed prior to the scheduled follow up period.

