8.11.11. Additional Safety Procedures

Additional non-invasive procedures that are already specified in the protocol may be performed, if it is believed that an important effect of the IMP(s) is occurring or may occur at a time when no measurements are scheduled, or if extra procedures are needed in the interests of safety.

Additional blood samples for safety assessments may be taken if required by the investigator at any point.

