## 7 ANALYSIS PLAN

## 7.1 General

Summary statistics for continuous variables will consist of the number of non-missing observations (n), mean, standard deviation (SD), minimum, 25th percentile, median, 75th percentile and maximum, unless specified otherwise. The precision of these variables is defined in the table, figure and listing shells document.

For categorical variables the number and percentage of subjects in each category will be presented, based on the number of non-missing observations apart from the disposition of subjects, protocol deviations, background and demographic characteristics, prior and concomitant medications/procedures and AEs where the percentage will be based on the number of subjects in the analysis set.

The number of missing observations will also be presented for each variable.

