#### 7.2.1 Baseline

For Parts 1 & 2 of the study, baseline is defined as the pre-dose value on Day 1. If that is missing it will be defined as the last non-missing value prior to the subject receiving study treatment (pre-dose) on Day 1.

For Part 3 of the study, within-period baseline is defined as the last non-missing value (including scheduled and unscheduled assessments) pre-dose on Day 1 for each of the respective study treatments. Overall baseline is defined as the pre-dose value on Day 1 of Period 1. If that is missing it will be defined as the last non-missing value prior to the subject receiving study treatment (pre-dose) on Day 1.

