#### 7.13.4 Pulmonary Function (Spirometry)

Spirometry observed values and change from baseline by parameter will be summarised over time. Parameters will be presented in the same order as the eCRF.

All spirometry data will be listed including change from baseline and reference ranges with flags to indicate all out of range values.

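### FEV1 and QTcF extremes seen only at unscheduled or repeat readings reach the listings but no spirometry or ECG table, and the SAP text plans no count against the protocol's QTcF limits

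*SAP*

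**What the plan says.** Spirometry and ECG are components of the primary safety endpoint (protocol 3.2.1, SAP 3.2.1).

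Under the general rule in SAP 7.5.3, tables take scheduled post-baseline readings only: "post-baseline repeat/unscheduled assessments will not be tabulated". The readings left out go to the listings. For lung function, SAP 7.13.4 says: "Spirometry observed values and change from baseline by parameter will be summarised over time". SAP 7.13.5 has the same plan for ECG, with replicates within one assessment averaged. Both sections list all data, with change from baseline and flags for values outside the reference ranges.

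The default statistics are in SAP 7.1: "Summary statistics for continuous variables will consist of the number of non-missing observations (n), mean, standard deviation (SD), minimum". That list continues through the quartiles and median to the maximum.

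The protocol generates off-schedule readings in four ways:
- Section 8.11.11 allows extra procedures if an important effect is suspected "at a time when no measurements are scheduled".
- Sections 8.11.9 and 8.11.10 require frequent FEV1 monitoring after treated bronchoconstriction until recovery to within 90% of baseline, or to a level the investigator accepts.
- Section 2.3.5 monitors lung function during sputum induction, with a stop at an FEV1 fall of 20% or more.
- Section 7.1 sets a withdrawal limit of "QTcF interval of >500 msec or increase in QTcF interval of >60 msec from baseline", judged on the triplicate mean and confirmed by a repeat triplicate.

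In Parts 2 and 3 spirometry after screening may be done before or after a bronchodilator; the Part 3 schedule says "there are no requirements for bronchodilator restrictions after the screening visit".

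**The concern.** Bronchoconstriction is the risk the protocol names for any inhaled product (2.3.3), and QTc prolongation is a named risk of voriconazole (8.12.6). Both are acute and may affect one subject in a small cohort. The readings most likely to document such an event are those prompted by suspicion, and the tabulation rule leaves those out.

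A reader of the report's spirometry and ECG tables would then not see, by dose, how far the worst-affected subject fell or how many subjects met the protocol's own QTcF limits. The answer would have to be assembled by hand from listings. Their flags refer to reference ranges, so a rise of more than 60 msec is not flagged as such.

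**Working it through.** The study is not powered and the plan gives no figure to reproduce on this point. The check has three steps.

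**1. Which Part 2 doses have scheduled post-dose spirometry?** Inputs are the Part 2 schedule and its footnotes (protocol 1.2.2).
- Day 1: 0.5, 2, 4 and 8 hours after the 0-hour dose (footnote r). Day 10: pre-dose and the same four times (footnote s).
- Day 2: 24 hours after the Day 1 dose and before the Day 2 dose (footnote h). Days 3 to 9: before the 0-hour dose only (footnote i).
- With twice-daily dosing, assessments are relative to the 0-hour dose only (footnote b).

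So two doses are followed by scheduled spirometry within 8 hours.
- Once daily: 10 − 2 = 8 of 10 doses without (80%).
- Twice daily: 19 − 2 = 17 of 19 doses without (89%).

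After those doses the next scheduled spirometry is about 24 hours later, or about 12 hours later for an evening dose. An acute fall in between could be measured only by an unscheduled test.

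**2. What would the by-visit table show?** Assume one subject has an excursion and all others have zero change. The sizes (−25% FEV1, +65 msec QTcF) are illustrative assumptions. FEV1 is shown in percent for readability; the SAP specifies change from baseline, not percent change.

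| Case | n | Mean change | Extreme shown |
|---|---|---|---|
| FEV1 −25% at a scheduled time | 6 | −25/6 = −4.2% | minimum −25% |
| FEV1 −25% at a scheduled time | 16 | −25/16 = −1.6% | minimum −25% |
| QTcF +65 msec at a scheduled time | 6 | 65/6 = 10.8 msec | maximum 65 msec |
| QTcF +65 msec at a scheduled time | 16 | 65/16 = 4.1 msec | maximum 65 msec |
| Either, seen only off schedule (for example FEV1 at 1 hour), normal at scheduled times | 6 or 16 | 0 | 0 |
| FEV1 fall treated, then 90% of baseline at the next scheduled test | 6 | −10/6 = −1.7% | minimum −10% |

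The mean dilutes a scheduled excursion, but the minimum or maximum shows it in full. An excursion seen only off schedule leaves no trace in either.

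**3. Do other tables fill the gap?**
- SAP 7.13.1.1 tabulates treatment-emergent events, including those leading to discontinuation, and SAP 7.6 tabulates reasons for withdrawal. Neither carries the measured value.
- An abnormal reading becomes an adverse event only if the investigator judges it clinically significant. Expected signs of the disease under study are excluded unless more severe than expected (protocol 10.3.1).
- Moderate or severe bronchospasm is an event of special interest, but SAP 7.13.1.2 makes that table conditional on need.
- No section of the SAP text plans a count against the QTcF limits or a worst post-dose value per subject.

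**The case against.** The case for leaving the plan alone is substantial, and much of it stands.

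- A reader might infer that the safety tables report only means and that threshold values never enter a primary-endpoint summary. They do not and can: minimum and maximum are default statistics, and adverse events are themselves part of the primary endpoint.
- For QTcF, if the triggering triplicate is a scheduled one it is tabulated, and only its confirmation is left out. Using the triplicate mean is not a defect, because protocol 7.1 defines its limit that way.
- A reader might also infer that the rule biases the primary safety result towards no effect. That needs an assumed sequence: onset before the 0.5-hour test, an unscheduled reading before salbutamol, then a recovered scheduled value. The documents give no frequency for it. Readings taken after treated bronchoconstriction are largely recovery values, and leaving those out does not favour the product.
- The 20% figure is a stopping rule for saline sputum induction, not a limit for drug effect. Mixing induction falls into a worst-value table could attribute them to the wrong cause.
- Part 3 within-period baselines admit unscheduled values. This is not an inconsistency: a baseline needs one last pre-dose value, and a by-visit table needs one value per nominal time.
- Everything is listed, and 6 to 16 subjects can be read by eye. Dose decisions rest on the Safety Advisory Committee's own data review (protocol 6.6.4), not on these tables (SAP 6).
- The table shells are a separate document (SAP 1), so an added categorical table cannot be ruled out.

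What remains is narrower. Values seen only off schedule enter no spirometry or ECG table, and SAP 7.5.3 as written would keep them out of any extra table in the shells too.

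**Conclusion.** The point holds as a reporting gap. Off-schedule FEV1 and QTcF extremes are kept in listings but summarised nowhere in the spirometry or ECG tables. The SAP text plans neither a count of subjects meeting the protocol 7.1 QTcF limits nor a worst post-dose FEV1 change per subject. The gap matters most in Part 2, where 80% of once-daily doses, or 89% of doses on the twice-daily regimen, have no scheduled spirometry in the following hours.

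The documents do not show that the reported safety result is biased, and no size can be put on how often a value would be missed. The conclusion rests on the SAP text alone, since the shells were not available, and on the Part 2 footnotes as read here. It is a cheap improvement.

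**What to change.** Keep the by-visit tables unchanged. Add an exception to SAP 7.5.3 for two descriptive tables, per dose in Parts 1 and 2 and per treatment in Part 3, that include unscheduled and repeat readings.

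1. **FEV1 (7.13.4).** Give the worst post-dose percent change per subject, with counts of falls of more than 10% and of 20% or more. Label these as descriptive cuts taken from figures the protocol already uses (8.11.9 to 8.11.10 and 2.3.5), not as limits for drug effect. Flag recent bronchodilator use and define the window; the 6 hours that protocol 6.5.3 uses for withholding short-acting agents at screening is one ready definition. Show readings taken during or after sputum induction separately.
2. **QTcF (7.13.5).** Count subjects with a triplicate-mean QTcF above 500 msec or an increase above 60 msec at any post-dose time, using the baseline in protocol 7.1 (per period in Part 3), and state whether the repeat triplicate confirmed it.

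The cost is a little programming on readings the SAP already lists, plus the care needed to identify induction-related falls and bronchodilator timing.
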